### 6.4 Previous use of Pirfenidone and Nintedanib

Previous use of pirfenidone and nintedanib will be recorded in the 'Pirfenidone/Nintedanib Usage' page of the CRF and will be summarized separately to other previous medications. Duration of treatment (up to date of randomization, for those on pirfenidone or nintedanib at baseline), time since end of treatment (where applicable) and reasons for discontinuation will be summarized.

	Plus-Project Statistical Analysis Plan	
	Protocol Number: GALACTIC-1	Version: 1

Summaries will be repeated for both the SoC1 / Combination and SoC2 / Monotherapy populations, and a supportive listing will be provided.

## 6.5 Prior and Concomitant Procedures

Data related to concurrent and post-treatment surgery or procedures in the ‘Surgery and Procedure’ eCRF will be coded using most recent up-versioned MedDRA coding as specified in the DMP.

The same definitions of concomitant and post-treatment will be applied as for medications (see Section 6.3).

Subject incidence of concurrent and follow-up surgery or procedures will be summarized separately, presented overall and by System Organ Class (SOC) and preferred term (PT). Within each separate summary, subjects will be counted only once for each SOC or PT if they have multiple records of the same SOC or PT term in the database.

## 7. STATISTICAL METHODS AND PRINCIPLES

This section describes the statistical analyses, presentation of the results, and the study endpoints that will be collected and/or derived during the study at the time points specified in the Schedule of Events (see Appendix 2 (Section 11.2)).

### 7.1 General Methods and Principles

#### 7.1.1 Analysis of Subgroups

Key subgroups for the study are:-

- Baseline FVC (%PRED): <80%, >=80%
- GAP index: I, II or higher
- Baseline GAL-3 level: < median, >= median\*
- Baseline MMP7: < median, >= median
- Gender (Female, Male)
- SoC treatment at baseline per eCRF (pirfenidone, nintedanib) for SoC1 / Combination Population only. Any SoC1 subject per the randomization who did not receive pirfenidone/nintedanib per the eCRF will be omitted from these subgroup analyses\*\*

\* Median baseline GAL-3 levels will be estimated per SoC population separately.

\*\* Only to be used for FVC (primary endpoint) and treatment compliance.

Other subgroups may be analyzed on inspection of the data.

	Plus-Project Statistical Analysis Plan	
	Protocol Number: GALACTIC-1	Version: 1

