## **5. GENERAL METHODS AND PRINCIPLES**

The SAP will be finalized and signed-off prior to DBL and unblinding. Any post-hoc analysis (analyses performed post DBL that are different from those described in the final version of the SAP) will be documented in the final clinical study report (CSR) as changes to the planned analysis.

All data collected will be listed, sorted by strata/treatment group, Subject ID, visit and time, with the Primary Population listed first as follows:-

- SoC2/Monotherapy Placebo,
- SoC2/Monotherapy GB0139 3 mg,
- SoC2/Monotherapy GB0139 10mg,
- SoC1/Combination Placebo,
- SoC1/Combination GB0139 3 mg,
- SoC1/Combination GB0139 10mg,
- Screening Failures.

Data on screening failures will be listed only.

Tabulations and data analyses will be performed using SAS® software, version 9.4 or later (SAS Institute, Inc.).

Unless otherwise specified, efficacy analyses will be performed in the mITT Analysis Set, with sensitivity analyses of the primary endpoints and secondary endpoints conducted using the PPS. Safety summaries will be performed using the SS Analysis Set. The ITT Analysis Set will be used to describe demographics, baseline characteristics and medical history.

The populations will be split according to SOC1 / Monotherapy and SOC2 / Combination, as well as per treatment group.

	Plus-Project Statistical Analysis Plan	
	Protocol Number: GALACTIC-1	Version: 1

P-values will be generated for all efficacy treatment comparisons, in all populations, as an exploratory tool for detection of potential contrasts in the material. P-values will not be generated for subgroup analyses.

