### 7.2.2.2 Subgroup Analysis

The primary analysis detailed in Section 7.2.1 will also be repeated by subgroup (separately for each subgroup factor of interest) for the Primary Population (52 week and 26 week endpoint) and the SoC1 / Combination Population (52 week and 26 week endpoint) in the mITT Set. The time by treatment group interaction will be replaced with a time by treatment group by subgroup interaction and fixed effect for the subgroup factor will also be added. The effect on slope between treatments will be assessed within each level of the subgroup.

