7.2.5.1 Biomarkers

Biomarker results will be provided by the central laboratory in standard units. The results, change from baseline and percentage change from baseline (for post baseline assessments) will be summarized by visit.

Correlation analyses assessing the relationship between Biomarker results and efficacy/safety endpoints may be performed.

7.2.5.2 Time to initiation of pirfenidone or nintedanib treatment for SoC2 subjects recruited to the original study design

Only the SoC2 / Monotherapy Population will be used, with only subjects recruited to the original study design (pre-Protocol V6.0).

The time to initiation of pirfenidone or nintedanib treatment will be derived from the 'Pirfenidone/Nintedanib Usage' eCRF. The time to initiation of pirfenidone or nintedanib treatment in weeks will be derived as (date of first initiation of pirfenidone or nintedanib treatment – date of randomization +1)/7.

Time to initiation will be summarized descriptively by treatment.

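### Effect modification by baseline galectin-3 and MMP7 is examined only through sample-median splits, which loses precision that a continuous-marker model would keep if the interaction is roughly linear

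*SAP*

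**What the plan says.** SAP 7.1.1 lists six key subgroups. Two are laboratory markers divided at the median: "Baseline GAL-3 level: < median, >= median" and "Baseline MMP7: < median, >= median". A footnote attached to galectin-3 alone adds that "Median baseline GAL-3 levels will be estimated per SoC population separately". The SAP does not say which population supplies the MMP7 median, and it gives no reason for cutting either marker at the median.

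For the FVC slope, SAP 7.2.2.2 states that "The time by treatment group interaction will be replaced with a time by treatment group by subgroup interaction", with a fixed effect for the subgroup factor. It then reports by level: "The effect on slope between treatments will be assessed within each level of the subgroup". This is done in the Primary and SoC1 / Combination populations, at 52 and at 26 weeks. The key secondary models in SAP 7.2.3.1 to 7.2.3.4 handle subgroups in a similar way.

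The markers are quantitative: "Biomarker results will be provided by the central laboratory in standard units" (SAP 7.2.5.1), with change and percentage change from baseline summarised. The only other analysis linking markers to outcome is optional and has no stated model: "Correlation analyses assessing the relationship between Biomarker results and efficacy/safety endpoints may be performed". SAP section 5 adds that "P-values will not be generated for subgroup analyses".

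**The concern.** GB0139 is a galectin-3 inhibitor, and Protocol 4.2.1 builds its rationale on galectin-3 being raised in IPF. It is therefore natural to ask whether the FVC effect grows or shrinks with baseline galectin-3, and the sponsor made this a key subgroup. MMP7 is a second biomarker of interest but not the drug's target.

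A median split treats two patients just either side of the cut as different, and treats a patient just above the cut and one at the extreme as the same. If the effect changes gradually with the marker, this discards usable information. With about 141 participants, the interaction is estimated imprecisely in any case. Since no subgroup p-values are produced, the estimate and its uncertainty are the whole output, so precision is what is at stake. A cut taken from the sample is also a poor threshold to carry into a later trial.

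**Working it through.** **Inputs.** From SAP 3.1: difference 100 mL, SD 240 mL, significance level 10%, N = 141, allocation 2:1, power 75%. Protocol 14.1 makes tests two-sided. I take 94 on 3 mg and 47 on placebo. This is illustrative, because the Primary Population also contains SoC2 subjects from the original design, who were randomised equally to 3 mg and placebo. The documents give no marker distribution and no interaction size, so those are assumptions and a range is shown.

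**1. The plan's own figure.** SE of the treatment difference = 240 × √(1/47 + 1/94) = 42.9 mL. Power = Φ(100/42.9 − 1.645) = Φ(0.687) = 75.4%; a t-based calculation gives 75.1%. The stated 75% reproduces.

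**2. Information kept by a median split.** For a linear effect of marker X, the share kept is the squared correlation between X and the indicator of being at or above the median. For a standard normal X:
- covariance = 1/√(2π) = 0.399
- SD of the indicator = 0.5
- correlation = 0.399/0.5 = 0.798
- share kept = 0.798² = 2/π = 0.637, a loss of 36.3%
- SE ratio = 1/√0.637 = 1.25
- equivalent sample size = 141 × 0.637 ≈ 90

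The share kept does not depend on the allocation ratio.

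**3. The same in mL.** With a continuous marker scaled to SD 1, the SE of the interaction is 42.9 mL per SD. With the split, the SE of the difference between halves is 2 × 42.9 = 85.8 mL. The halves of a normal marker have means 2 × 0.798 = 1.596 SD apart, so the split is equivalent to 85.8/1.596 = 53.7 mL per SD. The 90% CI half-widths are 1.645 × 42.9 = 70.5 mL and 1.645 × 53.7 = 88.4 mL per SD.

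**4. Simulation.** With N = 141, a normal marker, the sample median as the cut and 10,000 runs, the squared ratio of mean t statistics (split to continuous) was 0.625 for an interaction of 75 mL per SD and 0.615 for 100 mL per SD. That is a loss of 37–38%, in line with step 2.

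**5. Sensitivity to the assumptions.**

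| Marker distribution or effect (linear on the scale shown unless stated) | Information lost |
|---|---|
| Uniform | 25% |
| Normal | 36% |
| t, 5 df | 46% |
| Exponential | 52% |
| Lognormal on the raw scale, log-SD 0.3 / 0.5 / 0.8 / 1.0 | 41% / 48% / 63% / 73% |
| True effect a step exactly at the median | none |

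**The case against.** The strongest reply is that nothing in the trial turns on these analyses. They carry no p-values and do not touch the primary comparison. The protocol's own subgroup lists (14.4.1, 14.5 and 14.5.1) contain no biomarker, and no objective asks whether baseline galectin-3 predicts response. The link to mechanism is also indirect: Protocol 6.5 argues from galectin-3 on alveolar macrophages and lung exposure, whereas the baseline variable in SAP 6.2 is serum galectin-3. All of this stands and limits the weight of the point.

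Two stronger readings are tempting, and the documents support neither.

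- A reader might infer a loss of power. For an assumed interaction of 100 mL per SD, as large as the whole planned treatment effect, power at two-sided 10% would be 75% with a continuous marker and 59% after the split. At 50 mL per SD it would be 32% and 24%. But the SAP runs no interaction test, so these figures describe something that is not planned. At the smaller size neither analysis would tell much.
- A reader might infer that separate galectin-3 medians invalidate a comparison of the Primary and SoC1 populations. The SAP analyses them separately and plans no formal comparison, and a median per population keeps the halves balanced within each. What remains is that anyone setting the two displays side by side may be looking at different cut values.

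The optional correlations in SAP 7.2.5.1 mitigate only in part. They are not committed to, no model is given, and a correlation of marker with outcome does not estimate how the treatment effect varies with the marker.

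**Conclusion.** The point holds as a modest, inexpensive improvement to an exploratory analysis. It is not an error that affects the trial's conclusions. The SAP examines effect modification by baseline galectin-3 and MMP7 only through median splits and specifies no continuous treatment-by-marker model.

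The loss of about a third of the information, with a standard error about 25% larger, is conditional on a roughly normal marker on the analysis scale and a linear interaction. It should not be quoted without those conditions, because other shapes give anything from no loss to well over half. The documents give no basis for expecting a step at the median, the one case shown in which the split costs nothing. The consequence is lower precision in learning whether response depends on the marker.

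**What to change.** In SAP 7.2.2.2, for the FVC slope, add one model per marker for each analysed population and timepoint, with log2 baseline marker as a continuous term. Keep treatment, time and treatment × time, and add marker, marker × time, treatment × marker and treatment × time × marker. Report:

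- the treatment × time × marker coefficient per doubling of the marker, with its 90% CI, which means the same in every population;
- the 3 mg minus placebo slope difference at the same fixed marker values in every population, for example the pooled baseline quartiles, set before unblinding.

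Keep the median-split table for display and as a coarse check on log-linearity, setting the two half estimates beside the fitted line.

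Extension to the key secondary endpoints is optional. The logistic and Cox models would take a treatment × continuous marker term with no time terms.

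**Cost.** SAP wording before database lock and no new data. The FVC slope needs 2 populations × 2 timepoints = 4 models per marker, so 8 in all, with an additional arm to fit in SoC1. Covering the four key secondary endpoints in two populations would add at least 8 more per marker. The price in assumptions is log-linearity, and all the results remain exploratory.

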### 7.1.2 Methods for Handling Missing Values

In general, missing data will not be imputed. Exceptions are detailed in the subsequent sections.

### 7.1.3 Multiplicity

No adjustments for multiplicity are to be made in this study.

### 7.1.4 Pooling of Sites

No pooling of sites will be performed in this study.

## 7.2 Efficacy

All efficacy data described below will be summarized by visit including the change from baseline (when applicable).

### 7.2.1 Primary Efficacy Endpoint Analysis

The primary efficacy endpoint is the annual rate of decline in Forced Vital Capacity (FVC; expressed in mL over 52 weeks). Spirometry data provided by an external vendor showing the FVC (L) will be multiplied by 1000 to convert to mL. The analyses will be based on all FVC values obtained. Any FVC values post Day 453 will be omitted from the analyses.

The primary efficacy endpoint will be analyzed according to the estimand framework. Strategies for handling FVC data affected by the inter-current events (ICEs) of death, treatment discontinuation, and initiation of additional IPF therapy (pirfenidone or nintedanib) will be employed. Full details regarding use and imputation of FVC data in relation to ICEs are given in the next section.

### 7.2.2 Main Estimand and Analysis

The primary analysis will test for superiority of GB0139 3mg compared to Placebo (Plc) for the annual rate of decline in FVC in mL over 52 weeks in subjects not receiving pirfenidone or nintedanib at baseline in the mITT Set. The main estimand for the primary efficacy endpoint is as follows:

- Population: Primary Population, mITT set.
- Variable of interest: Change from baseline in FVC in mL over 52 weeks
- Intercurrent events:
  - Death: FVC attributed the lowest value recorded in the trial when a patient dies

	Plus-Project Statistical Analysis Plan	
	Protocol Number: GALACTIC-1	Version: 1

- Treatment Discontinuation: Analysis will include any FVC measurements after randomised treatment discontinuation
- Initiation of additional IPF therapy (nintedanib or pirfenidone): Analysis will include any FVC measurements after initiation of additional IPF therapy
- Summary measure: Comparison of slopes assessed through the treatment by time interaction.

The null hypothesis is:

$H_0$ : There is no difference in the annual rate of decline in FVC in mL between GB0139 3mg and Plc

The alternative hypothesis is:

$H_a$  : There is a difference in the annual rate of decline in FVC in mL between GB0139 3mg and Plc

A restricted maximum likelihood (REML) approach will be used, with a random coefficient regression (random slopes and intercepts) model fitted to test the hypotheses. The decrease in FVC is assumed to be linear within each subject over 52 weeks [5].

Baseline FVC and time will be fitted as continuous covariates. The treatment group and the interaction term for time by treatment group will be added as fixed effects. Random subject intercept and time effects will be fitted and will be assumed to be normally distributed with arbitrary covariance matrix. The within-subject errors will be assumed to be independent and normally distributed with mean zero and a common variance. The Kenward-Roger approximation will be used to estimate denominators degrees of freedom.

The statistical model will be as follows:

$$Y_{itk} = (\alpha + a_i + \tau_k) + \beta_f FVCb_i + (\gamma + \beta_3 T_3 + g_i) t + \varepsilon_{it}$$

where:

$Y_{itk}$  is the change from baseline measured for ith patient at time t (actual time) in treatment group k

$t$  is the time since randomization in years

$T_3 = 1$  if the subject is in the GB0139 3mg group, otherwise  $T_3 = 0$

$\beta_3$  is the effect of treatment on the slope compared to Placebo

$\alpha$  and  $\gamma$  are elements of the intercept and slope respectively

$a_i$  and  $g_i$  are random specific components of the intercept and slope respectively for the ith patient, assumed to be normally distributed with mean 0 and arbitrary covariance matrix

	Plus-Project Statistical Analysis Plan	
	Protocol Number: GALACTIC-1	Version: 1

$FVCb_i$  is the baseline FVC (mL) for the  $i$ th patient

$\tau_k$  is the intercept coefficient of the effect of treatment  $k$  ( $k=1, 2$ )

$\beta_f$  is the effect of 1ml increase in the baseline FVC

$\varepsilon_{it}$  is the random error for  $i$ th patient at time  $t$  assumed to be independent and normally distributed with mean 0 and variance  $\sigma^2$

This approach adopts a missing at random (MAR) assumption (i.e., the probability of an observation being missing depends only on observed measurements). Subjects with missing data at a particular time point still contribute to the analysis at that time point based on their other observed data used in the model (i.e., treatment, baseline FVC, and the FVC at baseline). Data that remain unobserved due to ICEs will be handled as described above. Other missing data will be imputed within the regression model under the MAR assumption.

The linearity assumption for the rate of change in FVC from baseline to week 52 will be explored graphically. Graphical displays will be provided of the mean ( $\pm$  SEM) observed FVC and mean change from baseline for each treatment group by visit.

The assumptions of the analysis will be checked by inspection of graphical displays of the residuals.

A cumulative distribution plot of the percentage of subjects by change from baseline in FVC in mL at week 52 will be presented.

The primary analysis detailed above will be repeated for the Primary Population, PP Analysis Set and for SoC1 / Combination and SoC2 / Monotherapy Populations (only for the mITT Analysis Set).

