14.4.1 Analysis of Primary Efficacy Endpoint

The primary endpoint is described in Section 9.1. The primary efficacy analysis is a random coefficient regression (random slopes and intercepts) model. Treatment and baseline FVC (mL) will be included as a covariate in the analysis model. Other covariates such as age, and gender will be included as covariates unless their inclusion violates model assumptions or impacts stability. Baseline FVC is defined as the FVC result recorded at Visit w0/baseline, unless missing in which case the latest FVC before randomization in the subject's chart result will be used.

The decrease in FVC is assumed to be linear within each subject over 52 weeks. The intercepts and slopes will be assumed to be normally distributed with arbitrary covariance matrix. The within-subject error will be assumed to be independent and normally distributed with mean zero and a common variance. The Kenward-Roger approximation will be used to estimate denominators degrees of freedom.

Section 14.8 details of the approaches to handling of missing data are given.

Significance tests will be based on least-squares means; p-values and two-sided 90% confidence intervals for the difference between the treatment groups will be presented. An intent-to-treat principle will be used. Analyses will be implemented using SAS® Version 9.4 or higher. The assumptions for the primary analysis of decline in FVC will be tested; details will be provided in the SAP. The primary analysis will be based on observed data (but including retrieved drop out

measurements) and will assume remaining missing data are missing at random. The effect of missing data will be investigated using multiple imputation methods which assume that subjects who discontinue treatment will no longer benefit from it in the future. See Section 14.8 for further details of these sensitivity analyses.

Subgroup analyses will be fully specified in the SAP and will include:

- Age
- Gender
- Race
- Ethnicity
- Previous treatment with pirfenidone and/or nintedanib
- Recruitment cohort (e.g., pre- or post- DSMB cutoff, and pre- or post-Protocol version 6.1_UK)

A cumulative distribution plot will be provided, showing the percentage of subjects by change from baseline in FVC in mL at week 52.

Data will be summarized graphically and using summary statistics.

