## 11.5 SAS Code

### 11.5.1 Primary analysis

```
ods output estimates=tests tests3=fixed;
proc mixed data=adef;
  where paramcd='FVC';
  class subjid trt01pn;
  model cfb = base areltn trt01pn trt01pn*areltn /ddfm=kr s residual outp=resplot;
  random intercept areltn / sub = subjid type = un;
  estimate 'Plc Slope' areltn 1 trt01pn*areltn 1 0/cl;
  estimate '3mg Slope' areltn 1 trt01pn*areltn 0 1/cl;
  estimate 'Slope 3mg v Plc' trt01pn*areltn 1 -1/cl;
run;
```

where

subjid = Subject ID

trt01pn = Randomized treatment group (1=Placebo, 2= GB0139 3mg)

base=Baseline FVC for the subject

areltn = Years since first dose

cfb = Change from baseline in FVC

<mean baseline FVC> = the mean of the variable base across all records in the dataset FVC relating to the population of interest (i.e. all records to be included in the model)

	Plus-Project Statistical Analysis Plan	
	Protocol Number: GALACTIC-1	Version: 1

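### Baseline FVC is a main effect only in the primary slope model, so it adjusts the intercept and gives the tested slope difference essentially no adjustment.

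*SAP*

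**What the plan says.** Protocol 14.4.1 specifies a random-intercept, random-slope model and says "Treatment and baseline FVC (mL) will be included as a covariate in the analysis model". It does not ask for an interaction between baseline and time.

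The SAP gives the model three times, and the three agree:

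- **Text, 7.2.2.** "Baseline FVC and time will be fitted as continuous covariates". Then: "The treatment group and the interaction term for time by treatment group will be added as fixed effects". No other time interaction is named.
- **Equation, 7.2.2.** The baseline coefficient, defined as what "is the effect of 1ml increase in the baseline FVC", stands outside the bracket that multiplies time. That bracket holds only the common slope, the treatment effect on slope and the patient's random slope.
- **Code, 11.5.1.** "model cfb = base areltn trt01pn trt01pn*areltn", with "random intercept areltn / sub = subjid type = un". There is no base*areltn term.

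The response is change from baseline in FVC at actual time. The summary measure in 7.2.2 is the treatment-by-time interaction. A death is scored with the lowest FVC recorded in the trial.

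**The concern.** A covariate without a time interaction changes the fitted level by the same amount at every visit. The trial tests a difference in slopes, so the only baseline covariate in the model does not act directly on the tested quantity. This is easily missed, because a model that lists baseline FVC reads as baseline-adjusted.

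It matters if decline in mL depends on baseline FVC. The part of the slope variance that baseline could explain then stays in the standard error, and a chance difference in mean baseline between 94 and 47 patients carries into the estimate. The documents do not say whether the disease produces such a link. The death rule does create one for patients who die: their change is the trial minimum minus their own baseline, so it falls by 1 mL for each extra mL of baseline.

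**Working it through.** **1. The plan's own figure.** Inputs from protocol 14.6 and SAP 3.1: difference 100 mL, SD 240 mL, two-sided alpha 10%, N = 141 at 2:1, taken as 94 and 47.

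- sqrt(1/94 + 1/47) = 0.1786
- SE = 240 × 0.1786 = 42.9 mL
- Power = Φ(100/42.9 − 1.645) = Φ(0.687) = 75.4%

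The stated 75% is reproduced. It assumes no gain from any covariate.

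**2. Does the main effect reach the slope difference?** Models without baseline, with the main effect (the SAP model) and with baseline-by-time added were fitted to simulated data: 47 against 94 patients, visits at weeks 4 to 52. The assumptions, none from the documents, are baseline SD 700 mL, random-slope SD 200 mL/yr, random-intercept SD 120 mL, residual SD 100 mL, and the dropout rates shown. Generalised least squares (GLS) with known variances used 60 data sets per setting. REML used 15.

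| Setting | Change in slope difference from adding the main effect |
|---|---|
| Complete data, common visit days | 0 to rounding; GLS SE 41.81 with or without it |
| Visit times varied by ±7 days | at most 0.05 mL/yr (GLS) |
| 25% dropout | at most 1.2, mean 0.2 mL/yr (GLS); at most 3.2, mean 1.0 mL/yr (REML) |
| 40% dropout | at most 2.1 mL/yr (GLS) |

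In the GLS runs with complete data, changing the intercept-slope correlation or including the week-0 record did not alter the zero.

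**3. Does that movement correct imbalance?** Suppose slopes are steeper by 50 mL/yr per litre of baseline.

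- SD of the chance imbalance = 700 × 0.1786 = 125 mL
- Expected shift in the slope difference = 0.05 × 125 = 6.3 mL/yr, about 0.15 of the SE (6.3/41.8)

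The simulated RMS shift was 6.17 mL/yr with complete data, both without baseline and with the main effect. With 25% dropout it was 6.37 in both. Adding baseline-by-time brought it to 0, given that the assumed dependence is linear. In the REML runs (60 mL/yr per litre assumed), baseline-by-time moved the estimate by a mean of 6.3 mL/yr and at most 18 with complete data, and by a mean of 8.2 and at most 26 with 25% dropout. Mean SE went from 42.10 to 41.53 with complete data, and from 47.16 (main-effect model) to 47.04 with dropout.

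**4. Power with baseline-by-time.** If ρ is the correlation of baseline FVC with slope, the residual SD is 240 × sqrt(1 − ρ²).

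| Assumed ρ | SD (mL) | Power |
|---|---|---|
| 0 | 240.0 | 75.4% |
| 0.1 | 238.8 | 75.8% |
| 0.2 | 235.2 | 76.9% |
| 0.3 | 228.9 | 78.8% |
| 0.4 | 220.0 | 81.6% |

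These figures ignore the cost of estimating one more coefficient. In the GLS runs, with the slope variance held fixed, that cost raised the SE from 41.81 to 41.96, about 0.4%.

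**5. The death rule.** If a proportion p of patients die, independently of baseline, and the substituted value is placed at week 52, mean change there falls by 1000 × p mL per litre of baseline through deaths alone: 50 mL at 5% and 100 mL at 10%. In about 30 simulated trials with 10% deaths and no other link (baseline SD 750 mL assumed), the main effect moved the slope difference by 0.03 mL/yr on average. Baseline-by-time moved it by 13 on average and at most 49. The SE fell only from 120.1 to 119.3, because the substituted values add much scatter of their own.

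**The case against.** The strongest reply is that nothing is wrong. Text, equation and code agree, and the protocol asks only for baseline FVC as a covariate. Under randomisation the slope comparison is valid without adjustment. Chance imbalance is already counted in the standard error and confidence interval, so the shift from imbalance and the lost precision are one cost seen twice. All of this stands. A reader might infer bias, an inflated type I error or a departure from the protocol; the documents support none of these.

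Nor is the slope difference wholly untouched by baseline FVC. The SAP uses actual times and keeps incomplete patients under missing at random, so the main effect enters the joint fit and moves the estimate slightly.

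A reader might also take the code legend, which defines "the mean of the variable base across all records in the dataset FVC" although no statement uses it, as the trace of a lost interaction. It would equally serve least-squares means from the present model, which protocol 14.4.1 mentions. It proves nothing either way.

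The SAP has related analyses. Baseline FVC below or above 80% predicted is a key subgroup (7.1.1) with its own slopes (7.2.2.2), and in the MMRM sensitivity analysis (7.2.2.4) baseline FVC does adjust the week-52 contrast. Neither adjusts the primary test.

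Finally, the gain rests on a correlation the documents do not give and may be near zero. The death argument concerns only patients who die, and a single linear term may not capture it fully. Both cautions stand.

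**Conclusion.** The point holds as a low-cost improvement and is not a correction of an error. In the primary model baseline FVC adjusts the intercept. It adjusts the tested slope difference by exactly nothing with complete data on common visit days, and by about 0 to 3 mL/yr under assumed dropout, without correcting imbalance.

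The possible gain runs from none at ρ = 0 to about 6 power points at ρ = 0.4 (75.4% to 81.6%), and is 1.5 points at ρ = 0.2. Under the assumed dependence of 50 mL/yr per litre, a typical chance imbalance shifts the estimate by about 6 mL/yr, which is small beside an SE of about 42. The correlation, variance components, dropout and death rates are all assumptions. The structural finding does not depend on them.

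**What to change.** Before unblinding:

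- Add a baseline-by-time term, with baseline FVC centred at its mean, to the equation in SAP 7.2.2 and as base*areltn in the model statement of 11.5.1.
- Estimate each arm's slope at mean baseline and say so in the text.
- Carry the term into the 26-week model in 7.2.2.1.
- In the subgroup model for baseline FVC (7.2.2.2), leave the term out or justify it, because it overlaps the subgroup-by-time term.

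If the sponsor prefers to keep the primary model, pre-specify the extended model as a sensitivity analysis and state that baseline FVC adjusts the intercept only. That is the smaller change, but the primary test then stays without slope adjustment.

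The cost is one model term, one degree of freedom and a sentence or two of text, with no new data. If the correlation is near zero there is no gain and a very slight loss of precision. Added after unblinding, the term would look chosen on the results.
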